9.3 Selection of Study Population

9.3.1 Inclusion Criteria

1. Male or non-pregnant, non-lactating females 12-17 years of age.
2. If female and of childbearing potential, prepared to abstain from sexual intercourse or use a reliable method of contraception during the study (e.g., condom, IUD, oral, transdermal or injected hormonal contraceptives). Female patients using hormonal contraceptives should have been on the same product/dosing regimen for at least 28 days before baseline and should not change this regimen during the study.
3. Signed IRB approved informed consent given by parent(s) or legally acceptable guardian(s) following their receipt of verbal and written information about the study. For patients age 12-17 years of age the child will be required to sign a patient “assent” form that will be written in such a way as to be understandable to a child.
4. Patients with a confirmed clinical diagnosis of stable plaque psoriasis of the scalp with $\geq 20\%$ scalp affected.
5. Investigator Global Assessment (IGA) score of 3 (Moderate) or 4(Severe)

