4. **HEENT Examination:** A general exam of the head, eyes, ears, nose and throat will be conducted at the clinic
5. **% Scalp Affected:** Patient's scalp will be examined by Investigator/designated clinician to determine the percent surface area affected with plaque psoriasis. Refer to Appendix B
6. **Investigator's Global Assessment:** Patient's scalp will be examined to determine a psoriasis severity score based on a global assessment of plaque elevation, scaling and erythema by the Investigator/designated clinician (refer to Appendix A).
7. **Concomitant Medication:** Review with the patient use of new or change in ongoing concomitant medication since Visit 2.
8. **Adverse Events:** Patients will be questioned about any health status changes/adverse events since last visit. All events will be recorded.
9. **Ocular Assessments:** Patients will be questioned about any ocular discomfort as a part of safety assessments (refer to Appendix C)
10. **Evaluation of Patient Compliance to the Protocol:** Collect and review patient's dosing diary for compliance.

CONFIDENTIAL PROTOCOL

An Open Label, Safety Study to Assess the Potential for Adrenal Suppression Following Maximal Use Treatment with Desoximetasone 0.25% shampoo(Taro Pharmaceuticals U.S.A., Inc.) in Patients with Scalp Psoriasis

11. **Collect Study Product:** The used bottle of study product will be collected and the weight recorded.
12. **Laboratory Evaluations:** A blood sample will be collected for hematology and clinical chemistry testing. (See Appendix F).
13. **Cortisol Response Test:** All patients will have a cortisol response test performed according to the procedure detailed in Appendix D.

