9.6.11 Pregnancy Test

Urine pregnancy tests on females of childbearing potential will be performed at Visit 1, 2, and 3. The test must be negative for the patient to be eligible for inclusion in the study. If the patient is of non-childbearing potential, the source document must list the reason why she is of non-childbearing potential (e.g., premenarchal).

Any patient who becomes pregnant during the study must be discontinued and End of Study procedures completed. The outcome of the pregnancy will be followed by the Investigator to birth or early termination as appropriate. The pregnancy will be reported as an AE.

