11.2.7 Pregnancies

Patients with a positive pregnancy test during screening will not be enrolled in the study. Patients who report that they have become pregnant during the study or have a positive pregnancy test at any clinic visit will be followed to completion of the pregnancy. The pregnancy will be reported as an AE.

Female patients of childbearing potential must have been using and must agree to continue to use accepted methods of birth control, throughout the study. All female patients are considered to be of childbearing potential unless they are premenarchal, have been surgically sterilized or have been postmenopausal for at least 1 year. Abstinence is an accepted method of birth control. Alternatively, any of the following methods of birth control are acceptable: oral contraceptives, contraceptive patches/implants (e.g., Norplant®), Depo-Provera®, double barrier methods (e.g., condom and spermicide) or IUD. Prior to study enrollment women of childbearing potential must be advised of the importance of avoiding pregnancy during study participation.

A negative result of a urine pregnancy test having a minimum sensitivity of at least 25 mIU/ml for hCG should be obtained, prior to study participation. Pregnancy testing will be performed at Visits 1, 2 and 3 and the results of all pregnancy tests (positive or negative) will be documented.

If following initiation of study treatment, it is subsequently discovered that a study patient is pregnant or may have been pregnant at the time of Investigational Product exposure, the Investigational Product will be permanently discontinued. The Principal Investigator must immediately notify the Medical Monitor of this event. Reporting timelines and Novum/Sponsor contact will be consistent with SAE reporting guidelines (see section 9.8.2 of the protocol), i.e., pregnancies will be reported to the Sponsor/Novum within 24 hours to the contacts listed in section 9.8.2.

CONFIDENTIAL PROTOCOL

An Open Label, Safety Study to Assess the Potential for Adrenal Suppression Following Maximal Use Treatment with Desoximetasone 0.25% shampoo(Taro Pharmaceuticals U.S.A., Inc.) in Patients with Scalp Psoriasis

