Protocol-required procedures for study discontinuation and follow-up must be performed on the patient. Other appropriate pregnancy follow-up procedures should be considered if indicated. In addition, the Principal Investigator must report to the sponsor follow-up information regarding the course of the pregnancy, including perinatal and neonatal outcome. Infants should be followed for a minimum of eight weeks after birth.

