Pregnancy Category C. Animal reproduction studies have not been conducted with CORTROSYN™ (cosyntropin) for Injection. It is also not known whether CORTROSYN™ can cause fetal harm when administered to a pregnant woman or can affect reproduction capacity. CORTROSYN™ should be given to a pregnant woman only if clearly needed.

Nursing Mothers

It is not known whether this drug is excreted in human milk. Because many drugs are excreted in human milk, caution should be exercised when CORTROSYN™ (cosyntropin) for Injection is administered to a nursing woman.

Pediatric Use

(See DOSAGE AND ADMINISTRATION section.)

ADVERSE REACTIONS

Since CORTROSYN™ (cosyntropin) for Injection is intended for diagnostic and not therapeutic use, adverse reactions other than a rare hypersensitivity reaction are not anticipated. A rare hypersensitivity reaction usually associated with a pre-existing allergic disease and/or a previous reaction to natural ACTH is possible. Symptoms may include slight whealing with splotchy erythema at the injection site. There have been rare reports of anaphylactic reaction. The following adverse reactions have been reported in patients after the administration of CORTROSYN™ and the association has been neither confirmed nor refuted:

- bradycardia
- tachycardia
- hypertension
- peripheral edema
- rash

DOSAGE AND ADMINISTRATION

CORTROSYN™ (cosyntropin) for Injection may be administered intramuscularly or as a direct intravenous injection when used as a rapid screening test of adrenal function. It may also be given as an intravenous infusion over a 4 to 8 hour period to provide a greater stimulus to the adrenal glands. Doses of CORTROSYN™ 0.25 to 0.75 mg have been used in clinical studies and a maximal response noted with the smallest dose.

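### Two sets of pregnancy rules need reconciling: condom-only and prior-use contraception at entry, and the Cortrosyn test in a patient found pregnant

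*Protocol*

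**What the plan says.** **Entry.** Inclusion criterion 2, worded alike in the synopsis and in Protocol 9.3.1, asks a female patient of childbearing potential to be prepared to abstain or "use a reliable method of contraception during the study (e.g., condom, IUD, oral, transdermal or injected hormonal contraceptives". Hormonal users must also have been on an unchanged regimen for at least 28 days before baseline. Protocol 11.2.7 says that such patients "must have been using and must agree to continue to use accepted methods of birth control, throughout the study". It accepts abstinence, oral contraceptives, patches or implants, an injectable and, for the rest, "double barrier methods (e.g., condom and spermicide) or IUD".

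**Pregnancy during the study.** Protocol 9.6.11: "Any patient who becomes pregnant during the study must be discontinued and End of Study procedures completed". Sections 9.3.4 (early discontinuation in general) and 11.2.7 (pregnancy) impose the same duty. The End of Study or Early Termination visit in 9.5.3 has, as item 13, "All patients will have a cortisol response test performed according to the procedure detailed in Appendix D". Appendix D carries out that test with an intramuscular Cortrosyn injection.

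**Cortrosyn.** Protocol 7.3 says the product will be used according to the manufacturer's instructions. The insert in Appendix G reports no animal reproduction studies, says it is not known whether the product can cause fetal harm, and says it "should be given to a pregnant woman only if clearly needed". Protocol 9.6.18 and Appendix D bar a repeat Cortrosyn test within 4 weeks of the last one. SAP Appendix D repeats the test procedure and this minimum, and also makes no provision for pregnancy.

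**The concern.** The protocol treats pregnancy as a real risk in these 12- to 17-year-olds: it is tested for at all three clinic visits and reported within 24 hours. Yet a site that follows the text can reach two answers on whether the same girl may enter. If it enrols her under inclusion criterion 2, she does not meet 11.2.7.

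The second problem concerns conduct after a positive test. The protocol adopts the manufacturer's instructions, then requires the injection as part of a fixed list of procedures, without the need test that those instructions attach to pregnancy. A site could inject a minor known to be pregnant because the checklist says so, or omit the injection and record a deviation. At stake are patient safety and consistent conduct, not the estimate of the suppression rate.

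**Working it through.** No sample size, power or error rate is involved. The check compares passages and makes one day count.

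**1. Contraception, side by side**

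| Situation | Inclusion 2 (synopsis, 9.3.1) | 11.2.7 |
|---|---|---|
| Abstinence | accepted | accepted |
| IUD | accepted | accepted |
| Oral, transdermal or injected hormonal | accepted, with 28 days of stable use | accepted, must already be in use |
| Condom alone | accepted (named example) | not listed; the barrier option is double barrier |
| Non-hormonal method started at enrolment | accepted (prepared to use) | not met (must have been using) |

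The sections part only in the last two rows. That inclusion 2 gives its methods as examples does not remove the first difference, because the condom is itself one of the examples. Exclusion criterion 1 speaks only of appropriate methods and so does not settle it.

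**2. The Cortrosyn chain**

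- A patient becomes pregnant: discontinue and complete End of Study procedures (9.6.11; also 9.3.4 and 11.2.7).
- End of Study procedures: cortisol response test for every patient (9.5.3, item 13).
- The test: Cortrosyn by intramuscular injection (Appendix D).
- Exemption or decision rule for a pregnant patient: none in either document.
- Manufacturer's condition, adopted by 7.3: in pregnancy, only if clearly needed (Appendix G).

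At Visit 3 the pregnancy test is item 2 and the cortisol test item 13. As listed, the positive result comes first.

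**3. Day count**

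- First Cortrosyn test: Day 1.
- Visit 2: Day 14 ± 2, that is, Day 12 to Day 16.
- Interval: 12 − 1 = 11 days to 16 − 1 = 15 days.
- Required minimum: 4 weeks = 28 days.
- Shortfall: 28 − 15 = 13 days to 28 − 11 = 17 days.

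Section 9.3.4 places the end-of-study procedures of an early discontinuation at the patient's last study visit. For a pregnancy found at Visit 2, that duty and the 4-week minimum cannot both be met at that visit. For patients whose Visit 1 test shows suppression, 9.6.18 does set a time, at least 28 days after the first test. There is no counterpart for pregnancy.

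**4. Does the analysis supply the need?**

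At one dose a day, a patient stopped at Visit 2 has had at most about 16 doses. Protocol 10.1.2 and SAP 6.2.1 require at least 21, so her test cannot enter the primary analysis. At Visit 3 a patient with 21 or more doses could count. Neither fact decides whether the test is clinically needed; the documents do not address that.

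**The case against.** The strongest reply is that these are narrow mismatches of wording. Much of it stands.

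- A reader might infer that 11.2.7 accepts double barrier and nothing else. It does not: abstinence, hormonal methods and IUD are accepted in both places. The 28-day rule in inclusion 2 also means that the difference over prior use leaves hormonal methods aside.
- A reader might infer that the insert forbids Cortrosyn in pregnancy. It does not. Its only contraindication is a previous adverse reaction; the pregnancy text is a caution. Whether an adrenal check after steroid exposure is clearly needed is a clinical judgement, and it may be.
- A reader might infer that sites are simply told to inject at Visit 2. The 4-week minimum speaks against that, so at Visit 2 the instructions pull in opposite directions.
- A reader might see a conflict over follow-up, because 9.6.11 follows the pregnancy to birth or early termination while 11.2.7 adds "Infants should be followed for a minimum of eight weeks after birth". These are separate duties for mother and infant, and a site can meet both.
- A reader might infer that the conflict costs endpoint data. Exclusion after a stop at Visit 2 follows from having fewer than 21 doses, and rewording would not recover it. At Visit 3 treatment is over, and a patient with enough doses and a test stays in the analysis.

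It can also be said that a site applying both contraception sections together breaks neither. That is true, but no text says that 11.2.7 narrows a method which the inclusion criterion names as reliable.

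**Conclusion.** Two contradictions hold on the current text. First, the eligibility criterion and 11.2.7 give different answers for a sexually active patient who relies on a condom alone or begins a non-hormonal method at enrolment. Second, the End of Study duty brings a Cortrosyn injection to a patient found pregnant without the need test in the instructions that the protocol adopts; at Visit 2 it also misses the 4-week minimum by 13 to 17 days.

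The number of patients affected is unknown. The documents give no figure for contraceptive practice or expected pregnancies; among the 5 to 10 patients planned it may be none, and no useful upper bound can be derived. The second point concerns positive results at two of the three scheduled tests (Visits 2 and 3) and any pregnancy reported during the study. It assumes that End of Study procedures in 9.6.11 means the list in 9.5.3, which is headed as the End of Study or Early Termination visit.

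The primary analysis is untouched. The matter is worth correcting for the safety of minors and for consistent conduct. Which contraceptive or testing rule is right is not judged here.

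**What to change.** - Reconcile inclusion criterion 2 (synopsis and 9.3.1) with 11.2.7, so that one list of accepted methods and one start requirement apply throughout.
- Reconcile 9.3.4, 9.5.3 item 13, 9.6.11 and 11.2.7 with the insert in Appendix G and with the 4-week minimum in 9.6.18 and Appendix D. State whether the Cortrosyn test is part of End of Study procedures for a patient with a positive pregnancy test, when it would be done if so, and who decides. Say also whether the repeat tests at 28, 56 and 84 days after an abnormal result are covered.
- Carry the result into SAP Appendix D, which copies the test procedure, and into the consent and assent text where it describes these rules.

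The clinical team chooses the rules; the statistical request is only that a site finds one answer. The cost is wording. The reconciliation itself calls for no additional patients, visits or analyses.

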9.3.2 Exclusion Criteria

1. Females who are pregnant, nursing, planning to become pregnant during the duration of the study, or if of child-bearing potential and sexually active and not prepared to use appropriate contraceptive methods to avoid pregnancy.
2. Patients < 12 years of age or > 17 years of age.
3. Patients whose scalp psoriasis necessitates systemic or other concomitant topical therapies during the study. Concomitant treatment of body psoriasis with OTC topical products, including emollients, is allowed.
4. IGA score < 3 .
5. Scalp psoriasis with $< 20\%$ scalp affected.
6. History of psoriasis that has been unresponsive to topical corticosteroid therapy.
7. Patient has a scalp skin condition that would interfere with the diagnosis or assessment of plaque psoriasis of the scalp (e.g., seborrheic dermatitis, eczema, cutaneous T-cell lymphoma, or other forms of psoriasis including guttate, inverse, pustular or erythrodermic psoriasis).

CONFIDENTIAL PROTOCOL

An Open Label, Safety Study to Assess the Potential for Adrenal Suppression Following Maximal Use Treatment with Desoximetasone 0.25% shampoo(Taro Pharmaceuticals U.S.A., Inc.) in Patients with Scalp Psoriasis

8. History of an adverse reaction to CortrosynTM or similar test reagents
9. Presence of pigmentation, extensive scarring, pigmented lesions, or sunburn in the treatment areas that could interfere with the rating of efficacy parameters, including planned extensive exposure to sunlight during the study.
10. History of allergy or sensitivity to corticosteroids or history of any drug hypersensitivity or intolerance which, in the opinion of the Investigator, would compromise the safety of the patient or the results of the study.
11. Patient has a significant history or current evidence of chronic infectious disease, system disorder, organ disorder or insufficiency, immunosuppression (from medical treatment or disease), organ transplant or other medical condition that, in the Investigator's opinion, would place the study patient at undue risk by participation in the study.
12. Patient is currently receiving or has received any radiation therapy or anti-neoplastic agents within 3 months before baseline.
13. Known history of hypothalamic-pituitary-adrenal axis impairment or any other disturbance of the adrenal function (e.g. Cushing or Addison disease).
14. Known or suspected severe renal insufficiency or severe hepatic disorders or severe heart disease.
15. Patients who have a history of or current diagnosis of glaucoma or posterior subcapsular cataracts or any other ocular condition that, in the opinion of the Investigator, would place study patient at undue risk.
16. Patients who have had surgery on the eyes or eyelids within 1 month before baseline or plan to have eye or eyelid surgery during the study.
17. Patients with active infection (including but not limited to bacterial, fungal and viral infection) and/or open wounds on the entire head and neck area.
18. Use within 4 weeks before baseline of 1) oral or intravenous corticosteroids, 2) UVA/UVB therapy, 3) PUVA (psoralen plus ultraviolet A therapy, 4) topical tacrolimus, 5) topical pimecrolimus, 6) systemic retinoids or 7) any other systemic psoriasis treatment
19. Use of tanning booths or nonprescription UV light source within 2 weeks before baseline.
20. Use within 8 weeks before baseline of 1) immunomodulators or immunosuppressive therapies or 2) interferon.
21. Use within 14 days before baseline of calcipotriene or other Vitamin D preparations.
22. Changed brands/types or frequency of use of routine hair care products (shampoo, conditioner, sprays etc.) within 14 days before baseline, or intend to change during the study.
23. Use of systemic antibiotics or prescription-strength systemic anti-inflammatory agents within 1 month before baseline.
24. Use of the following within 2 weeks before baseline:
 - a. Topical anti-psoriatic agents.

CONFIDENTIAL PROTOCOL

An Open Label, Safety Study to Assess the Potential for Adrenal Suppression Following Maximal Use Treatment with Desoximetasone 0.25% shampoo(Taro Pharmaceuticals U.S.A., Inc.) in Patients with Scalp Psoriasis

- b. Topical corticosteroids.
- c. Topical retinoids.
- d. Topical anti-inflammatory agents.
- e. Medicated shampoos for scalp psoriasis (including coal tar shampoo).
- f. New regimens of beta blockers.
- g. Lithium preparations.
- h. Anti-malarial agents.

25. Patient has been treated within 12 weeks before baseline with any biological therapies for psoriasis.

26. Inability to understand the protocol requirements, instructions, and study-related restrictions, the nature, scope, and possible consequences of the clinical study.

27. Unlikely to comply with the protocol requirements, instructions, and study-related restrictions, such as uncooperative attitude, inability to return for follow-up visits, and improbability of completing the clinical study.

28. Receipt of any drug as part of a research study within 30 days before baseline.

29. The patient is a member of the investigational study staff or a member of the family of the investigational study staff.

30. Previous participation in this study.

9.3.3 Restrictions during the Study

The following concomitant medications will not be allowed while enrolled in the study:

Restricted medication	Examples (not comprehensive)	Wash out
Topical corticosteroids (on scalp or body), retinoids or anti-inflammatory agents (on scalp)	Topicort® (desoximetasone 0.25%) spray, Cortaid® (hydrocortisone 1%), Clobex® (clobetasol 0.05%), Diprolene® (betamethasone 0.05%), retinol, diclofenac, etc.	2 weeks
Topical anti-psoriatic medication (on scalp)	Psorcon® ointment/cream, Dovonex® (calcipotriene), Tazorec® (tazarotene), Vectical® (calcitriol), salicylic acid, anthralin, coal tar, etc., including medicated shampoos	2 weeks
Beta blockers, lithium preparations, anti-malarial agents or tanning booths	metoprolol, labetalol, Eskalith, Lithobid, quinine, etc.	2 weeks

CONFIDENTIAL PROTOCOL

An Open Label, Safety Study to Assess the Potential for Adrenal Suppression Following Maximal Use Treatment with Desoximetasone 0.25% shampoo(Taro Pharmaceuticals U.S.A., Inc.) in Patients with Scalp Psoriasis

Biologic treatment for psoriasis	Remicade® (infliximab), Enbrel® (etanercept), Humira® (adalimumab), etc.	12 weeks
Chemotherapy Radiation therapy		3 months
Systemic corticosteroids Systemic antipsoriatic treatment Systemic antibiotics PUVA therapy UVB therapy Prescription strength systemic anti-inflammatory agents	Prednisone (Short and occasional use of intranasal, inhaled or ophthalmic corticosteroids for acute and transitory conditions [e.g. allergic rhinitis] up to 1 mg per day is acceptable) methotrexate, cyclosporine, hydroxyurea *the use of acetylsalicylic acid for prophylactic use up to 325 mg/day is allowed, provided that the patient is on a stable dose for at least 3 months and the regimen will remain constant throughout the study	4 weeks
Systemic retinoids	Soriatane® (acitretin), Isotretinoin etc	4 weeks
Systemic immunosuppressive drugs	tacrolimus, pimecrolimus	8 weeks

Patients and will be advised to avoid environmental conditions that may exacerbate their disease state. Patients will be advised to avoid exposure to sunlight of a duration that would require application of sunscreen.

In addition, patients must have consistently used a single brand/type of hair care product (e.g., shampoo, conditioner, spray, etc.) for a minimum of 14 days prior to baseline. Patients will be asked to continue using the same brand/type and frequency of use throughout the study.

Patients will be questioned about all concomitant prescription and OTC medication use at each study visit. All concomitant medications will be recorded in the patient's study chart. Any patient who violates any of the listed restrictions should be dropped from continued participation in the study by the Investigator.

